#### **16.2.4. ANALYSIS OF KEY SECONDARY EFFICACY ENDPOINTS**

Method to control the overall type 1 error is described in [Section 7.4](#).

##### **16.2.4.1. Change from Baseline in Quantitative SARS-CoV-2**

The first key secondary efficacy goal is to provide greater reduction in quantitative SARS-CoV-2.

The analyses will summarize log10 quantitative SARS-CoV-2 at each required scheduled timepoint. Missing data will not be imputed. Separate summaries will be performed for:

- All subjects who have baseline quantitative SARS-CoV-2 above the limit of quantification.
- All subjects who have baseline quantitative SARS-CoV-2 above the median.

Document: \[REDACTED]\net\enterprise\Apps\sasdata\SASb\SAS\Atea\_Pharmaceuticals\AT-527\1SZA63631\Biostatistics\Documentation\SAP\AT-03A-001\_V1.0\_COVID\_SAP\_PA7.doc

Author: \[REDACTED] Version Number: V1.0

Version Date: 15Apr2021

Template No.: CS\_TP\_BS016 Revision 6

Reference: CS\_WI\_BS005

Effective Date: 02Dec2019

Copyright © 2009, 2010, 2012, 2016, 2018, 2019 \[REDACTED] All rights reserved. The contents of this document are confidential and proprietary to \[REDACTED] Holdings Inc. and its subsidiaries. Unauthorized use, disclosure or reproduction is strictly prohibited.

- All subjects who have baseline quantitative SARS-CoV-2 above 4 log10 copies/mL.
- All subjects who have baseline quantitative SARS-CoV-2 above 6 log10 copies/mL.

For each summary, observations reported as below the limit of quantitation (LOQ) by the quantitative TaqPath assay will be assigned a value each of the method below:

- Method 1:
  - Above LOD by TaqPath: TaqPath LOQ-1.
  - Below LOD by TaqPath: TaqPath LOQ/2.
- Method 2:
  - If non detectable by COBAS and below LOD by TaqPath: COBAS limit of detection (LOD) /2
  - If detectable by COBAS: TaqPath LOQ/2

Quantitative laboratory parameters reported as “> X”, i.e. above the upper limit of quantification (ULQ), will be converted to X for the purpose of quantitative summaries. For samples reported outside the limits of quantification, listings will display “< X” or “> X”, as appropriate.

The analyses will compare change from baseline log10 quantitative SARS-CoV-2 at each required scheduled timepoint. Any missing data will not be included in the analyses. Change from baseline quantitative SARS-CoV-2 will be compared between the AT-527 group and the placebo group at each of days 2, 5, and 14 using ANCOVA with treatment as a factor and log10 baseline quantitative SARS-CoV-2 as a covariate. For each time point and LOQ handling method, the least squares mean (LSM) change and its standard error of means (SE) in each group, the differences between two groups in LSM change with corresponding 95% confidence intervals (CIs), and p-values will be presented. Statistical significance at Day 2 and Day 5 will be assessed based on two-sided 0.025 level test to account for 2 comparisons. The formal statistical comparison will be based on Method 1.

The raw and LSMs change from baseline in log10 will also be presented graphically over time.

#### 16.2.4.2. Time to Clinical Recovery (days) by Day 14

Another key secondary efficacy goal is to shorten the median days to clinical recovery (MDCR) by at least 4 days for active-dosed subjects compared to placebo recipients during the 14-day primary study period. The median times

Document: \[REDACTED]\net\enterprise\Apps\sasdata\SASb\SAS\Atea\_Pharmaceuticals\AT-527\5ZA63631\Biostatistics\Documentation\SAP\AT-03A-001\_V1.0\_COVID\_SAP\_PA7.doc  
Author: \[REDACTED] Version Number: V1.0  
Template No.: CS\_TP\_BS016 Revision 6 Version Date: 15Apr2021  
Effective Date: 02Dec2019 Reference: CS\_WI\_BS005

Copyright © 2009, 2010, 2012, 2016, 2018, 2019 \[REDACTED] All rights reserved. The contents of this document are confidential and proprietary to \[REDACTED] Holdings Inc. and its subsidiaries. Unauthorized use, disclosure or reproduction is strictly prohibited.

to clinical recovery will be presented for each treatment group as well as the number and percentage of subjects with and without clinical recovery. The Wilcoxon Mann-Whitney test will be used to test that there is no difference between the treatment groups by a one-sided  $\alpha=0.025$  p-value.

As a sensitivity analysis a Kaplan-Meier curves (product-limit estimate) will be provided by treatment arm for the time to clinical recovery (days). Subjects will be censored as follows:

- If subject dies without clinical recovery, censor at Day 15
- If subject has no post-baseline scale, censor at Day 1
- If no clinical recovery censor at the last day (date of the last non-missing scale score, prior to and including Day 14)

Kaplan-Meier estimates of the time will be provided at the 25th, 50th (median), and 75th percentiles along with their corresponding two-sided 95% CIs. The estimates of the SEs will be computed using the Greenwood's formula, the CI for the median will be calculated according to Brookmeyer and Crowley (1982), and the CIs for the survival function estimates will be derived from the Kaplan-Meier estimates using the log-log transformation.

The p-value associated with the log-rank test statistic will be provided and compared at the one-sided 0.025 alpha level based on a null hypothesis that there is no difference between the two treatment groups and will be presented for descriptive purpose only.

#### 16.2.4.3. Proportion of Subjects with RFD by Day 28

The secondary key efficacy endpoint of proportion of subjects with RFD by Day 28 will be analyzed similarly to the primary efficacy endpoint as described in [Section 16.1.3](#). The one-sided p-value will be calculated to test the null hypothesis that the proportion of subjects with RFD on and before Day 28 is less in the treated group.

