8.3.2. Key Secondary Analyses

Change from baseline in amount of quantitative viral load (Part A only)

Viral load will be assessed quantitatively using a validated assay. The analyses will compare change from baseline log10 viral load at each required scheduled timepoint. Only patients with measurable viral load at baseline will be included in the analyses. Change from baseline viral load will be compared between the AT-527 group and the placebo group at each of Days 2, 5, and 14 using ANCOVA with treatment as a factor and log10 baseline viral load as a covariate. The least

Protocol Number: AT-03A-001

squares mean (LSM) change and its standard error of means (SE) in each group, the differences between two groups in LSM change with corresponding 95% confidence intervals (CIs), and p-values will be presented. Statistical significance will be tested at Day 5, which is a time point with required sample collection in all versions of the protocol, using on one-sided 0.025 level test. If statistical significance is observed at Day 5, then Day 2 would also be tested. The Day 14 comparison will be descriptive. Descriptive summaries and comparisons at non-required timepoints may also be presented.

Median Days to Clinical Recovery

The Wilcoxon Mann-Whitney test will be utilized for the first key secondary endpoint analysis because the distribution of days until clinical recovery is not anticipated to be normally distributed.

Proportion of Subjects with Respiratory Failure or Death

This secondary endpoint will be analyzed in the same fashion as the primary endpoint, as it is similarly a proportion analysis.

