## COVID-19 Statistical Analysis Plan

ATEA Pharmaceuticals  
Protocol AT-03A-001

Page 20 of 77

log10 copies/mL, then there is at least 85% power to detect a 1 log10 greater reduction in viral load using a two-sided level 0.05 test, i.e. a one-sided level 0.025 test. The corresponding statistical hypotheses are as follows:

- $H_0$ : Experimental change from baseline  $\geq$  Control change from baseline
- $H_a$ : Experimental change from baseline  $<$  Control change from baseline

Second Key Secondary Efficacy Endpoint: Median days to Clinical Recovery (MDCR), from randomization to a disease resolution status in the NIAID Clinical Status scale described in the protocol Section 6.9 - i.e. achieving Clinical Status 6, 7, or 8 by Day 14, according to whether the subject is still hospitalized at Day 14 or is an outpatient. Patients without observed clinical recovery will have clinical recovery time assigned as 15 days to preserve the ranks for the comparison.

The power assessment for this endpoint assumed days to clinical recovery in the control and experimental arms have exponential distributions. If the median time to recovery is 12 days for the placebo arm, then a one-sided 0.025 level test has 80% power to detect a 5 day reduction in median recovery time with the experimental arm (i.e. median is 7 days for experimental arm). If these assumptions hold, we would expect to observe approximately 50 and 68 clinical recoveries in the placebo and experimental arms, respectively, during the 14 day follow-up. The study statistical hypotheses are as follows:

- $H_0: \text{ExperimentalMDCR} \geq \text{ControlMDCR}$
- $H_a: \text{ExperimentalMDCR} < \text{ControlMDCR}$

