## 7.3. STATISTICAL TESTS

All statistical tests will be conducted at the two-sided 5% significance level (i.e. 2.5% for one-sided tests), unless otherwise specified in the description of the analyses. Confidence Intervals (CIs) will be two-sided with 95% coverage.

[figure not shown]

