## 7.4. MULTIPLE COMPARISONS/ MULTIPLICITY

A sequential gatekeeping strategy will be utilized for the primary and the secondary efficacy endpoints to maintain the one-sided Type 1 error rate at  $\alpha=0.025$ . The efficacy objectives will be tested in the following order:

- (1) The primary efficacy endpoint of proportion of subjects with PRI in the ITT analysis set will be tested at one sided  $\alpha = 0.025$ .
- (2) If the primary efficacy comparison achieves statistical significance, there may be two comparisons for the first key secondary endpoint. The comparison at Day 5 will be tested first at one-sided  $\alpha=0.025$ . If statistical significance is met on the Day 5 comparison, then the quantitative SARS-CoV-2 changes at Day 2 would be formally tested at one-sided  $\alpha=0.025$ .
- (3) The second key secondary endpoint of median days to clinical recovery will be tested at one sided  $\alpha = 0.025$  only if the primary efficacy objective and the first key secondary objective are met for Day 5 and Day 2 (at one-sided  $\alpha=0.025$ ).
- (4) The final key secondary endpoint of proportion of subjects with respiratory failure or death will be tested at one sided  $\alpha = 0.025$  only if both the primary efficacy objective and the first and second key secondary objectives are met (at one-sided  $\alpha=0.025$ ).

Document: \[REDACTED]\net\enterprise\Apps\sasdata\SASb\SAS\Atea\_Pharmaceuticals\AT-527\SAZ\A63631\Biostatistics\Documentation\SAP\AT-03A-001\_V1.0\_COVID\_SAP\_PA7.doc  
Author: \[REDACTED] Version Number: V1.0  
Template No.: CS\_TP\_BS016 Revision 6 Version Date: 15Apr2021  
Effective Date: 02Dec2019 Reference: CS\_WI\_BS005

Copyright © 2009, 2010, 2012, 2016, 2018, 2019 \[REDACTED] All rights reserved. The contents of this document are confidential and proprietary to \[REDACTED] Holdings Inc. and its subsidiaries. Unauthorized use, disclosure or reproduction is strictly prohibited.

Only nominal two-sided p-values will be provided for the other secondary and the exploratory efficacy endpoints.

No statistical testing will be performed for the safety endpoints.

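### SAP 16.2.4.1 tests Day 2 and Day 5 viral load at two-sided 0.025, but SAP 7.4, which governs these tests, sets a fixed sequence at one-sided 0.025

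*SAP*

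**What the plan says.** Two parts of the SAP set a significance level for the same two comparisons.

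- **SAP 16.2.4.1 (analysis of change from baseline):** "Statistical significance at Day 2 and Day 5 will be assessed based on two-sided 0.025 level test to account for 2 comparisons". It gives no testing order.
- **SAP 16.2.4 (its parent section):** "Method to control the overall type 1 error is described in" Section 7.4.
- **SAP 7.4, step 2:** "The comparison at Day 5 will be tested first at one-sided" α = 0.025. Day 2 is then tested at one-sided 0.025, but only if Day 5 is significant.
- **SAP 7.4, step 3:** clinical recovery is tested "only if the primary efficacy objective and the first key secondary objective are met for Day 5 and Day 2", again at one-sided 0.025.

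The other relevant text agrees with 7.4. The power statement for this endpoint in SAP 7.1 assumes "a two-sided level 0.05 test, i.e. a one-sided level 0.025 test". Protocol 8.3.2 and the synopsis give one-sided 0.025 for Day 5 and the same order: "If statistical significance is observed at Day 5, then Day 2 would also be tested". Neither states a level for Day 2. SAP 7.3 sets the default, "All statistical tests will be conducted at the two-sided 5% significance level", but lets the description of an individual analysis override it.

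**The concern.** The sentence in 16.2.4.1 describes an equal split of alpha over two comparisons. Section 7.4 describes a fixed sequence, in which each test keeps the full one-sided 0.025 because the second is reached only after the first succeeds. The reason given for the split does not apply to that procedure.

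Because 7.3 gives way to the description of an analysis, a programmer could follow 16.2.4.1 in good faith while another statistician follows 7.4. The same Day 5 result could then be called significant or not, depending on which section was read. Part A viral load is the signal the protocol cites for going on to Part B, so two written thresholds for it should not stand side by side once data have been seen. The changes form of 16 March 2022 does not settle this: its ANCOVA entries concern the display of p-values and of least squares means, not the test level.

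**Working it through.** **Inputs.** SAP 7.1: 182 subjects allocated 1:1; 90% with quantifiable baseline viral load; difference 1 log10; SD of change 2 log10; power stated as at least 85%. Protocol synopsis: enrollment goal 190. SAP 16.2.4.1: ANCOVA with log10 baseline as covariate.

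**1. The two levels.** Two-sided 0.025 puts 0.0125 in the direction of benefit.
- Section 7.4: z(0.975) = 1.960.
- Section 16.2.4.1: z(0.9875) = 2.241.

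**2. Type 1 error of each rule (one-sided).**
- Split as in 16.2.4.1: at most 0.0125 + 0.0125 = 0.025.
- Fixed sequence as in 7.4: no claim is possible unless Day 5 passes at 0.025, and Day 2 is then tested at 0.025. The family-wise error is therefore at most 0.025 (simulated 0.0249 to 0.0251).
- Full level on both days without the order: 1 − 0.975² = 0.049 if the tests are independent, and about 0.039 at correlation 0.8. A correction must therefore carry over the order as well as the level.

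**3. The plan's own power figure.** Evaluable per arm = 182 × 0.9 / 2 = 81.9. With no gain from baseline adjustment, SE = 2 × √(2/81.9) = 0.3125 and 1/SE = 3.20.
- At the 7.4 level: Φ(3.20 − 1.960) = 0.892 (noncentral t 0.889). This meets the stated minimum of 85%.
- At the 16.2.4.1 level: Φ(3.20 − 2.241) = 0.831 (noncentral t 0.825). This falls short of it.
- With 190 enrolled (85.5 per arm): 0.905 and 0.848.

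**4. Where the calls differ.** The smallest significant Day 5 difference is 1.960 × 0.3125 = 0.61 log10 under 7.4 and 2.241 × 0.3125 = 0.70 log10 under 16.2.4.1. Results between these values get opposite calls.

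**5. Effect of baseline adjustment.** If change correlates with baseline at r, the residual SD is 2 × √(1 − r²). Power at the 16.2.4.1 level, 81.9 per arm:

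| r | Power (normal approximation) |
|---|---|
| 0 | 83.1% |
| 0.22 | about 85% |
| 0.3 | 86.7% |

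By noncentral t, 85% is reached at r of about 0.25. The documents give no correlation, so r is an assumption.

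**The case against.** The strongest defence is that 16.2.4.1 is a deliberate, stricter level. Section 7.3 allows an analysis description to depart from the default, and a stricter test cannot inflate error. It is true that the sentence is no slip of the pen, since it gives its own reason. But 7.4 sets a level for these same two tests, and 16.2.4 names 7.4 as the controlling section, so the exception in 7.3 does not decide between them.

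The second defence is that little depends on it. That stands, and it sets the weight of the point.

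A reader might infer more than the documents support:

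- **Inflated type 1 error.** No. Each rule alone holds the one-sided error at 0.025.
- **A harder route to clinical recovery.** Step 3 of 7.4 fixes that gate itself, at one-sided 0.025 on both days. Section 16.2.4.1 says nothing about gating, so its level should not be carried into it.
- **The stated power holds only under 7.4.** Not established. It does so with no gain from the covariate, but a modest baseline correlation brings the stricter test to 85%.
- **16.2.4.1 contradicts its own intervals.** It does say "the differences between two groups in LSM change with corresponding 95% confidence intervals (CIs), and p-values will be presented". However, 7.3 prescribes 95% intervals throughout, and an unadjusted interval beside a stricter test is a permitted presentation.
- **The interim result turns on this.** The reported 0.7 log10 is a Day 2 difference. The readable text gives no Day 5 estimate with a standard error, so nothing shows that an observed result lies in the gap.

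**Conclusion.** The inconsistency is real and unresolved; its severity is minor. Section 16.2.4.1 uses z 2.241 where the governing rule uses 1.960. A Day 5 one-sided p-value between 0.0125 and 0.025 therefore receives opposite calls. At planning values the cost of the stricter level is about 6 percentage points of power (89% against 83%), assuming SD 2, about 82 per arm and no gain from baseline adjustment.

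The practical consequence is small for three reasons.

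- Under 7.4 the viral-load test is formal only after PRI succeeds, and the Amendment 8 rationale in Protocol 1.1 accepts that this is futile.
- SAP 4.2 allows efficacy results to be treated as exploratory after the interim disclosure, and Protocol 8.2.2 calls all analyses descriptive. The synopsis confines the loss of formal error control to Part B and keeps the Part A hierarchy. That tension is separate, and this conclusion does not depend on how it is settled.
- The changes form says the study is ending early and that the interim tables and figures serve as the final delivery.

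**What to change.** In SAP 16.2.4.1, replace the whole sentence that sets two-sided 0.025, including its reference to two comparisons, with: *Day 5 and Day 2 are tested in the order and at the one-sided 0.025 level given in Section 7.4.* Both order and level must be carried over, because the level alone would not control the error.

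The changes form states that the SAP will not be updated, so the practical route is one entry in that form. Both timing options on the form fall after unblinding. The entry should therefore say that it is a post-unblinding correction, that it restores the pre-specified rule in 7.4 of SAP version 1.0, and that it relaxes the threshold written in 16.2.4.1.

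No estimate, interval or p-value changes. The only real cost is openly disclosing that a threshold was relaxed after unblinding.

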### Third Key Secondary Efficacy Endpoint: Respiratory failure or death

The next key secondary efficacy endpoint of the study is the proportion of subjects with Respiratory Failure or Death (RFD), for which the featured assessment will be at Day 28, with additional analyses at Days 10, 14, and 63. Assuming the RFD rate (RFDR) is 0.35 and 0.15 in the control and experimental arms, respectively, at alpha one-sided of 0.025, at a total of 182 subjects with a 1:1 allocation, i.e. 91 per study arm, the power is 85%. The study statistical hypotheses are as follows:

- $H_0: \text{ExperimentalRFDR} \geq \text{ControlRFDR}$
- $H_a: \text{ExperimentalRFDR} < \text{ControlRFDR}$

Document: \\[REDACTED]\net\enterprise\Apps\sasdata\SASb\SAS\Atea\_Pharmaceuticals\VAT-527\ISZA63631\Biostatistics\Documentation\SAP\VAT-03A-001\_V1.0\_COVID\_SAP\_PA7.doc  
Author: [REDACTED] Version Number: V  
Template No.: CS\_TP\_BS016 Revision 6 Reference: CS\_WI\_BS016  
Effective Date: 02Dec2019

Copyright © 2009, 2010, 2012, 2016, 2018

Copyright © 2009, 2010, 2011  
Proprietary to [REDACTED] Holdings

Proprietary to [REDACTED] Holdings Inc. and its subsidiaries. Unauthorized use, disclosure or reproduction is strictly prohibited.

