### 16.1.3. PRIMARY ANALYSIS OF PRIMARY EFFICACY ENDPOINT

The primary efficacy goal is to reduce the incidence of PRI by 50% for active-dosed subjects compared to placebo recipients. Number and proportion of subjects with and without PRI during the 14-day primary study period will be provided by treatment group based on the ITT analysis set. The difference between the treatment groups will be presented with corresponding 95% CI. A Cochran-Mantel-Haenszel (CMH) general association test will be used to test for differences in rates between the treatment groups controlling for geographic region (see [Section 7.6](#)).

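### SAP 16.2.4.3 states the null hypothesis for respiratory failure or death (RFD) in the opposite direction to SAP 7.1, so the SAP contradicts itself on the direction of a one-sided key secondary test

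*SAP*

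**What the plan says.** **SAP 7.1** (third key secondary endpoint) sets out the formal hypotheses. The null is that the experimental RFD rate is greater than or equal to the control rate; the alternative is that it is lower. The planning statement agrees: "Assuming the RFD rate (RFDR) is 0.35 and 0.15 in the control and experimental arms, respectively", with one-sided alpha 0.025, 91 subjects per arm and a stated power of 85%.

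**SAP 7.4** places RFD last in the gatekeeping order, at one-sided 0.025.

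**SAP 16.2.4.3**, the section that defines the analysis, says that RFD "will be analyzed similarly to the primary efficacy endpoint as described in" Section 16.1.3. It then requests a p-value in one direction only and gives the purpose as follows: "to test the null hypothesis that the proportion of subjects with RFD on and before Day 28 is less in the treated group".

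**SAP 16.1.3**, to which it refers, gives one test: "A Cochran-Mantel-Haenszel (CMH) general association test will be used to test for differences in rates between the treatment groups controlling for geographic region". It also asks for the treatment difference with a 95% CI. It gives no rule for obtaining a one-sided p-value.

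**The concern.** A p-value measures evidence against the null. If the null is that RFD is less frequent on AT-527, a small p-value is evidence that AT-527 does worse, and a real benefit gives a p-value near 1. That is the reverse of what SAP 7.1 and 7.4 intend for an efficacy objective.

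The sentence sits in the section a programmer would open to code the test, so it is an instruction and not background text. A second, smaller gap makes it harder to resolve from that section alone. The test named in 16.1.3 carries no direction, so nothing in its output would show which tail was meant.

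**Working it through.** **1. Reproduce the plan's own figure.** The inputs from SAP 7.1 are 0.35 (control), 0.15 (experimental), 91 per arm and one-sided 0.025. Protocol Appendix 1 specifies Fisher's exact test.

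- Exact power, by enumerating both binomial distributions and rejecting when the lower-tail Fisher p is at most 0.025: 85.3%.
- Arcsine approximation with continuity correction: power = Φ(h·√(n/2) − 1.960), where h = 2[asin√(0.35 − 1/182) − asin√(0.15 + 1/182)].
  - h = 2(0.6273 − 0.4053) = 0.444 and √45.5 = 6.745, so h·√(n/2) = 2.994.
  - Power = Φ(2.994 − 1.960) = Φ(1.034) = 84.9%.

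Both agree with the stated 85%. The figure holds only in the 7.1 direction. Rejecting in the other tail at the same rates, exact power is about 6 × 10⁻⁸ (about 9 × 10⁻⁸ by normal approximation).

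**2. Set the two hypotheses side by side.**

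| Section | Null | Alternative |
|---|---|---|
| SAP 7.1 | experimental ≥ control | experimental < control |
| SAP 16.2.4.3 | lower in the treated group | not stated |

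The null in the second row is the alternative in the first.

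**3. Put numbers on the two readings.** Take the nearest whole counts to the planning rates: 0.15 × 91 ≈ 14 events on AT-527 and 0.35 × 91 ≈ 32 on placebo, 46 in all. Region sizes are not given, so one stratum is assumed.

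- Expected events on AT-527: 91 × 46/182 = 23.
- Variance: 91 × 91 × 46 × 136/(182² × 181) = 8.641.
- Signed root: z = (14 − 23)/√8.641 = −3.06.
- CMH statistic: Q = z² = 9.37 on 1 df, two-sided p = 0.0022.
- One-sided p with the 7.1 null (lower tail): 0.0011.
- One-sided p with the literal 16.2.4.3 null (upper tail): 1 − 0.0011 = 0.9989.

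**4. Check whether the CMH statistic can settle the direction.** Swap the arms: z becomes +3.06, but Q stays 9.37 and the two-sided p stays 0.0022. The statistic has no sign. Halving its p-value without looking at the direction of the difference amounts to rejecting whenever the two-sided p is at most 0.05. That test has size 0.05, of which 0.025 lies in the direction of harm.

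**The case against.** The strongest reply is that this is one badly worded sentence. SAP 7.1 has the formal hypotheses the right way round, the power calculation depends on them, and 7.4 treats RFD as an efficacy objective. A statistician reading the whole SAP would know which tail was meant. This stands, and it limits the point to a contradiction within the SAP.

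A reader might infer that following the SAP gives the wrong tail, so that benefit returns 0.99 and harm is declared significant. The documents do not support this. The named test has no direction and cannot return 0.9989 by itself. Someone would have to add a sign rule that the SAP does not contain and then choose the direction opposite to 7.1.

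A reader might also extend the fault to the primary endpoint, progressive respiratory insufficiency (PRI), which uses the same CMH test. That goes too far. The PRI hypotheses in 7.1 are correctly directed, and 16.1.3 contains no reversed null and no request for a one-sided p-value. It reports the difference with its 95% CI, which shows direction. SAP 7.3 pairs two-sided 5% with one-sided 2.5%. With two arms and a binary outcome the statistic has 1 df, so a two-sided p below 0.05 with the difference favouring AT-527 corresponds to one-sided 0.025. For PRI a written rule is a convenience.

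Finally, the result may never be used. The changes form lists RFD by Day 28 among the outputs not presented and displays two-sided p-values for everything except ANCOVA. Protocol 8.2.2 keeps the hierarchy for historical perspective and calls the analyses descriptive, although the synopsis still describes alpha-preserving testing in Part A. This also stands as a limit on consequence. It does not remove the error: both timing options printed on the form fall after unblinding, the form does not mention the reversed null, and it says the SAP will not be updated.

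**Conclusion.** The point holds as an internal contradiction. SAP 16.2.4.3 names as the null what SAP 7.1 names as the alternative, for a key secondary test set at one-sided 0.025. Taken literally, the analysis section replaces the intended one-sided p with 1 minus p. The example with 14 and 32 events rests on the single-stratum assumption, but the argument about direction does not depend on it.

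The missing conversion from the CMH p-value is a secondary clarification. It leaves the direction unstated; it does not create a wrong tail.

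The practical effect on the final delivery is small, for the reasons given above. The documents give no ground for inferring that a reported result is in the wrong direction, since no RFD by Day 28 output is presented under the changes form.

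**What to change.** In SAP 16.2.4.3, replace the null with the one in 7.1: the RFD rate on AT-527 is greater than or equal to the rate on placebo, against the alternative that it is lower.

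Add one sentence on the p-value. The one-sided p is half the two-sided CMH p when the stratum-adjusted difference favours AT-527, and 1 minus that half otherwise. This is the signed root of the 1-df statistic. The same sentence can serve PRI.

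The cost is two sentences. Design, data, sample size and power do not change. Since the changes form says the SAP will not be updated, the correction could be recorded as a dated note alongside that form.
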